12.2.2.4 Assessment of Outcome

The result or conclusion of the AE will be assessed and recorded by the Investigator as:

- Fatal

- Not recovered/not resolved (the AE has not improved or patient has not recuperated).
- Recovered/resolved (the AE has improved or patient has recuperated)
- Recovered/resolved with sequelae (recuperated but retained pathological conditions resulting from the AE)
- Recovering/resolving (the patient is improving but the AE has not yet resolved)
- Unknown (not known, not observed, not recorded, or refused)

12.2.2.5 Action Taken with Study Drug

The action taken with reference to study drug will be assessed by the investigator as:

- Dose not changed (dose completed)
- Dose interrupted (IV infusion was temporally modified by temporarily stopping the infusion; slowing of the rate of infusion should also be classified as interrupted)
- Drug withdrawn (IV infusion was modified through termination of the infusion)

A response option for increasing or decreasing the dose is not an available course of action in this study.

12.2.2.6 Laboratory and Diagnostic Abnormalities as Adverse Events

Clinically significant abnormal laboratory findings or other abnormal diagnostic assessments (e.g., ECGs, vital signs) that are detected in dosed patients or that significantly worsen relative to baseline in dosed patients will be reported as AEs. Clinical significance is based on the Investigator's judgment but will typically include findings that result in study withdrawal, result in active management of the patient, or are associated with clinical signs and symptoms. Since the study requires patients with elevated or abnormal SUA levels, abnormal SUA levels will typically not be an AE unless judged by the Investigator as being more severe than expected for the patient.

12.2.2.7 Pregnancy

While pregnancy itself is not considered to be an AE, any pregnancy complication or elective termination of a pregnancy for medical reasons will be recorded as an AE and followed. The outcome of all pregnancies must be followed up and documented even if the patient is no longer a study patient.

The Investigator, or his/her designee, will collect pregnancy information on every female who becomes pregnant while enrolled in this study and on every female partner of a male patient who becomes pregnant while the male partner is enrolled in this study. The Investigator will report to the Sponsor or Sponsor's designee within 24 hours of learning of a patient's or female partner of a patient's pregnancy. In the case of a female partner of a male patient enrolled in the study becoming pregnant while the male patient is enrolled in this study, a separate pregnancy partner informed consent form will be completed by the patient's partner. The patient or female partner

of a patient must also be followed to determine the outcome of the pregnancy. Information on the status of the mother and child will be forwarded to the Sponsor or Sponsor Designee, as appropriate. Follow-up on the child will be to the first well-child visit. Any premature termination of the pregnancy will be reported.

A spontaneous abortion or congenital abnormalities/birth defects will be considered SAEs and will be reported as such. Furthermore, any SAE occurring as a result of a post-study pregnancy and is considered reasonably related to the study drug by the Investigator, will be reported to the Sponsor.

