7. INVESTIGATIONAL PLAN

7.1 Overall Study Design

This study is a randomized, open-label, parallel-arm study to compare the safety and efficacy profiles of SEL-212 and KRYSTEXXA. Approximately 150 patients will be randomized 1:1 prior to Baseline to receive treatment with SEL-212 or KRYSTEXXA for 6 months. Efficacy assessments, as measured by SUA levels, will be conducted at intervals that are appropriate to determine treatment effect differences, including at month 3 and month 6. Assessments of qualitative endpoints will be conducted on an assessor-blinded basis. Safety will be monitored throughout the study.

The study will be divided into 3 study periods: Screening, Treatment, and Follow-up, described below. The study is depicted schematically in [Figure 1](#).

The total duration of participation in the study will range from approximately 26 to 31 weeks (184 to 219 days) for patients randomized to SEL-212 and approximately 28 to 33 weeks (198 to 233 days) for patients randomized to KRYSTEXXA as follows:

- Screening and/or washout and premedication period: up to 45 days (up to 6.5 weeks)
- Treatment: 168 days (24 weeks) for SEL-212 KRYSTEXXA
- Safety Follow-Up: 30 (+ 4) days after the date of last infusion
 - SEL-212: Last scheduled infusion on Study Day 140
 - KRYSTEXXA: Last scheduled infusion on Study Day 154

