7.1.3 Follow-Up Period

Patients will be followed for safety monitoring for 30 (+ 4) days after their final study drug infusion and will have an End of Study visit by telephone. Patients who terminate the study prematurely will have all Early Termination assessments performed. Patients who terminate the study prematurely who are unable to be on-site for the Early Termination visit will be contacted by telephone for safety follow-up.

Figure 1: Study Schematic

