8.2.1.2 Patient Completion

A patient will be considered to have completed the study when the patient has completed Safety Follow-up that occurs 30 (+ 4) days after the final dose of study drug. Enrolled patients who prematurely discontinue for any reason before completion of the study will be treated as outlined below in [Section 8.2.1.3.1](#).

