12.1.8.8 Pregnancy Screen

Samples for urine pregnancy testing (hCG) will be obtained.

Female partners of male patients who are of childbearing potential are required to practice an acceptable form of birth control to continue in the study and for 30 days after the last study drug administration. Male patients of reproductive potential who are having intercourse with female partners of childbearing potential must agree to use 2 forms of contraception, 1 of which must be a barrier method, during the study and for 90 days after the last study drug administration.

Acceptable barrier methods include a condom and diaphragm. Acceptable forms of birth control for female partners of childbearing potential are non-hormonal and hormonal intrauterine devices, hormonal birth control pills, hormonal birth control patches, hormonal birth control injections, hormonal birth control implants. Spermicide used alone is not an acceptable method and must be used with another acceptable form birth control method. Abstinence is acceptable if consistent with the patient's normal lifestyle.

If a patient becomes pregnant after she begins taking study drug, the procedures in [Section 12.2.2.7](#) should be followed.

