12.2.3 Reporting Adverse Events

12.2.3.1 Adverse Event Reporting Period

The study period during which AEs must be reported is from the time the patient is dosed until the 30 days after the last infusion of study drug. During the Screening Phase (from time informed consent is signed up to the time of dosing) any clinically significant changes in the patient's health will be recorded in the patient's medical history and will not be considered as AEs.

Investigators are not obligated to actively seek AEs or SAEs in former study patients. However, if the Investigator learns of any SAE, including a death, at any time after a patient has been discharged from the study, and he/she considers the event reasonably related to the study drug, the Investigator should promptly notify the Sponsor.

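### Partner pregnancies must be collected only while the male patient is enrolled, which after a full course ends 30 (+4) days post-dose, although male contraception is required for 90 days

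*Protocol*

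**What the plan says.** **Contraception (Protocol 12.1.8.8).** Male patients of reproductive potential with partners of childbearing potential must use two methods, one of them a barrier, "during the study and for 90 days after the last study drug administration". The sentence before it requires the female partners to use an acceptable method "to continue in the study and for 30 days after the last study drug administration".

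**Pregnancy collection (Protocol 12.2.2.7).** For partners, the investigator collects pregnancy information "on every female partner of a male patient who becomes pregnant while the male partner is enrolled in this study". The separate partner consent form carries the same enrolment condition. The section also has three provisions without that condition:

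- a 24-hour report to the sponsor once the investigator knows of a patient's or partner's pregnancy;
- follow-up of the outcome of all pregnancies, including after the patient has left the study;
- a report of any SAE arising from a post-study pregnancy that the investigator judges related to study drug.

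**End of participation.** Under Protocol 8.2.1.2 a patient completes the study when "the patient has completed Safety Follow-up that occurs 30 (+ 4) days after the final dose of study drug". Section 7.1.3 agrees: "Patients will be followed for safety monitoring for 30 (+ 4) days after their final study drug infusion". AEs are reportable "from the time the patient is dosed until the 30 days after the last infusion of study drug" (12.2.3.1), and that section does not oblige investigators to look actively for events in former patients.

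**Patients withdrawn from drug (7.4.1.1 and 7.4.1.2).** They keep attending visits to the end of Treatment Period 6.

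**The concern.** Inclusion criterion 4 admits only women of non-childbearing potential, so a partner pregnancy is in practice the main way an exposed pregnancy could arise. The protocol asks the man to take precautions for 90 days after his last dose, but its explicit duty to collect partner pregnancies stops when he leaves the study, about 30 days after that dose if he completes the course.

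For a partner pregnancy that begins later, the only explicitly post-study duty is the SAE report, which depends on the investigator learning of the event and judging it related. Normal outcomes, and adverse ones judged unrelated, need not clearly be recorded. A related SAE could then appear with no count of exposed pregnancies to set it against. Few pregnancies are likely, so each one missed is a real loss of safety information.

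**Working it through.** **Inputs**

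- Last scheduled infusion: Study Day 140 for SEL-212 and Day 154 for KRYSTEXXA (Protocol 7.1).
- Safety follow-up: 30 to 34 days after the last infusion (7.1.3, 8.2.1.2).
- Maximum screening: 45 days (7.1).
- Post-dose contraception periods: 90 days for male patients and 30 days for female partners (12.1.8.8).
- End of Treatment Period 6: nominal Day 168 (168 days of treatment, 7.1).

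**Step 1. Reproduce the plan's participation totals.** Maximum = screening + last infusion day + 34.

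- SEL-212: 45 + 140 + 34 = 219 days, as stated.
- KRYSTEXXA: 45 + 154 + 34 = 233 days, as stated.

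The stated minimums are 184 = 140 + 30 + 14 and 198 = 154 + 30 + 14. They fit if screening lasts at least 14 days, which the text does not say. The totals confirm that participation ends 30 to 34 days after the last scheduled dose.

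**Step 2. Gap for a full course.** Uncovered days = 90 minus post-dose days enrolled.

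| Arm | Enrolment ends | 90-day period ends | Uncovered |
|---|---|---|---|
| SEL-212 | Day 170–174 | 140 + 90 = Day 230 | 56–60 days |
| KRYSTEXXA | Day 184–188 | 154 + 90 = Day 244 | 56–60 days |

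60/90 = 66.7% and 56/90 = 62.2%, the same in both arms.

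**Step 3. Gap for patients withdrawn from drug but followed.** Enrolment is assumed to end at the later of Day 168 and last dose + 30 days.

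| Last dose | Study Day | Post-dose days enrolled | Uncovered of 90 |
|---|---|---|---|
| SEL-212, TP1–TP3 | 0–56 | 112 or more | 0 |
| SEL-212, TP4 | 84 | 84 | 6 (6.7%) |
| SEL-212, TP5 | 112 | 56 | 34 (37.8%) |
| KRYSTEXXA, infusions 1–6 | 0–70 | 98 or more | 0 |
| KRYSTEXXA, infusion 7 | 84 | 84 | 6 (6.7%) |
| KRYSTEXXA, infusion 8 | 98 | 70 | 20 (22.2%) |
| KRYSTEXXA, infusion 9 | 112 | 56 | 34 (37.8%) |
| KRYSTEXXA, infusion 10 | 126 | 42 | 48 (53.3%) |
| KRYSTEXXA, infusion 11 | 140 | 30 | 60 (66.7%) |

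A patient who leaves the study altogether soon after a dose could have a gap above 67%, because enrolment would then end before day 30 post-dose.

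**Step 4. Against the 30-day period.** Enrolment covers 30 to 34 post-dose days, so the gap is 0.

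**Step 5. Whether other provisions close the gap.** The 24-hour rule and the outcome rule have no end date. The first applies only when the investigator learns of a pregnancy. The second can be read as covering only pregnancies that the enrolment-limited sentence brings in. Neither extends the partner consent, which outcome data would need. The end-of-study call covers concomitant medications and procedures, AEs and SAEs (Appendices A and C, note 1). Pregnancy is not on that list, and 12.2.2.7 says that pregnancy is not in itself an AE.

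**The case against.** **The undated rules may already do the work.** Read generously, the 24-hour rule and the all-outcomes rule reach any partner pregnancy the investigator hears of, whenever it begins. A reader might infer from the enrolment condition that later pregnancies would be neither registered nor followed, and that the study would report none. The text does not support that: it is ambiguous, not silent. What remains is that collection and consent, the two operative steps, are expressly tied to enrolment.

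**The two contraception periods bind different people.** The 30 days applies to the partner, who needs one acceptable method. The 90 days applies to the man, who needs two. Both can be met, so calling them a flat contradiction goes too far. They still fit badly: most of the acceptable methods listed in 12.1.8.8 other than the barrier methods are ones the partner uses, and her stated obligation ends at 30 days while his two-method obligation continues.

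**The size depends on the yardstick.** This is correct. Against 30 days there is no gap. Section 12.1.8.8 gives no rationale for 90 days, so it does not follow that the protocol regards the later weeks as a time of established reproductive risk.

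**Other documents may cover it.** Consent pages were not available for this review, nor was the Study Operations Manual. Patients may already be told to report later partner pregnancies. That would help in practice but would leave 12.2.2.7 unclear.

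**The stakes are limited.** The number of men with partners of childbearing potential is not given, eligibility runs to age 80, and the SAP describes no pregnancy analysis. That is fair, and it argues for a wording change and nothing larger.

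**Conclusion.** The point stands as a mismatch between 12.1.8.8 and 12.2.2.7. For a patient who takes the last scheduled dose, 56 to 60 of the 90 post-dose days (62% to 67%) fall outside required partner-pregnancy collection, in both arms.

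That figure rests on three assumptions: the 90-day period is the reference, the last scheduled dose was taken, and enrolment ends at the 30 (+4) day contact. A reader might take two-thirds as applying to every patient. It does not: the stopping rules can end dosing early, and most such patients who stay in follow-up have a smaller gap or none.

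This is a matter of safety-data completeness. Sample size, type I error and the primary analysis are unaffected. No view is taken on which contraception period is right.

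**What to change.** 1. Reconcile the 30-day and 90-day periods in 12.1.8.8 with each other and with 12.2.2.7. The duration is for the sponsor to decide.
2. In 12.2.2.7, replace the enrolment condition in both the collection sentence and the partner-consent sentence with an explicit reporting period aligned to the reconciled post-dose contraception period. State that the 24-hour report and the outcome follow-up apply throughout it.
3. At the existing end-of-study telephone call, ask male patients to report any partner pregnancy until that date.

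If collection ran through the 90-day period, the uncovered part would fall from 56–60 days to 0. The cost is amended protocol and consent wording and a few later reports, received passively through existing sites and forms. No extra visit is needed.

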12.2.3 Reporting Adverse Events

12.2.3.1 Adverse Event Reporting Period

The study period during which AEs must be reported is from the time the patient is dosed until the 30 days after the last infusion of study drug. During the Screening Phase (from time informed consent is signed up to the time of dosing) any clinically significant changes in the patient's health will be recorded in the patient's medical history and will not be considered as AEs.

Investigators are not obligated to actively seek AEs or SAEs in former study patients. However, if the Investigator learns of any SAE, including a death, at any time after a patient has been discharged from the study, and he/she considers the event reasonably related to the study drug, the Investigator should promptly notify the Sponsor.

12.2.3.2 SAE Reporting Procedures

If SAEs occur, all Investigators should immediately, but not later than 24 hours of observing or learning of the event, complete and fax the SAE form to Syneos Health and Pharmacovigilance.

Facsimile (for SAE only): [REDACTED]

Email (for SAE only): [REDACTED]

The Investigator will complete the SAE form and provide all case information available at the time of the initial report. The investigator must include the following mandatory case information:

1. The patient identification number
2. The event description
3. The seriousness criteria
4. The Investigator's causality assessment

The reporting Investigator must send the written and signed SAE report by facsimile or email, within 24 hours of observing, notification of, or learning of the SAE to Syneos Health and Pharmacovigilance as described above. Follow-up information regarding an SAE and the supporting data, including laboratory findings and discharge summaries, should be sent by

facsimile or email to Syneos Health and Pharmacovigilance within 24 hours of receipt of the information.

If the Investigator does not have all information regarding an SAE, the Investigator will not wait to receive additional information before completing as much of the form as possible and notifying the safety group. The form will be updated when additional information is received. The Investigator will always provide at minimum: 1) AE term or event name/description, 2) patient identifier, 3) an assessment of causality ([Section 12.2.2.2](#)).

12.2.3.3 Regulatory Reporting Requirements for SAEs

The Sponsor or Sponsor representative will report fatal or life-threatening SAEs that are unexpected suspected adverse reactions to the relevant regulatory authorities within 7 calendar days, and non-fatal or life-threatening SAEs that are unexpected suspected adverse reactions within 15 calendar days as Investigational New Drug (IND) Safety Reports, in accordance with 21 CFR 312.32. Prompt notification of SAEs by the Investigator to the appropriate project contact for SAE receipt is essential so that legal obligations and ethical responsibilities towards the safety of other patients are met.

12.2.3.4 Reporting Safety Information to the IRB/IEC

The Investigator, or responsible person according to local requirements, will comply with the applicable local regulatory requirements related to the reporting of SAEs to the Institutional Review Board (IRB)/Ethics Committee (EC).

All Investigators involved in studies with this drug will receive a copy of each IND Safety Report. When an Investigator receives an IND Safety Report or other safety information (e.g., revised Clinical Investigator's Brochure/Investigator's Brochure), the responsible person according to local requirements is required to promptly notify his or her IRB.

12.2.4 Follow-up of Adverse Events

The Investigator is required to proactively follow each patient and provide further information in regards to AEs and SAEs. All AEs and SAEs will be followed until 30 days after the last dose of study drug, resolution of the event, until the condition stabilizes, until the event is otherwise explained, or until the patient is lost to follow-up, whichever occurs earlier. Once resolved, the appropriate CRF entries and event reporting forms will be updated, as appropriate.

All AEs and SAEs documented at a previous visit/contact and designated as ongoing will be reviewed at subsequent visits/contacts. The Investigator will ensure that follow-up includes any supplemental investigations as may be indicated to elucidate the nature and/or causality of the AE or SAE. This may include additional laboratory tests or investigations, histopathological examinations, or consultation with other health care professionals.

STUDY: SEL-212/202
VERSION: 3.0

EFFECTIVE DATE

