7.4.1 Safety Criteria for Adjustment or Stopping Doses

7.4.1.1 SEL-212

A patient randomized to treatment with SEL-212 will be withdrawn from study drug for meeting the following stopping rule:

- In the SEL-212 arm: SUA level > 1.0 mg/dL measured at the Day 21 visit of Treatment Period 1 or SUA level > 6.0 mg/dL at the Day 21 visit of Treatment Periods 2, 3, 4, or 5

The window for all Day 21 visits is -2/+1 days.

If a Day 21 visit SUA value drawn within the protocol window is not available, but if a SUA value drawn at an unscheduled visit after the Day 21 window is available prior to dosing that is ≤ 1.0 mg/dL during Treatment Period 1 or ≤ 6.0 mg/dL during Treatment Periods 2, 3, 4, or 5, the patient will not be required to be withdrawn from study drug and may be eligible to receive their subsequent dose.

If 1) a Day 21 visit SUA value drawn within the protocol window is not available and no subsequent SUA results are available or 2) a Day 21 visit SUA value drawn within the protocol window is not available and a subsequent SUA drawn at an unscheduled visit after the Day 21 window is > 1.0 mg/dL during Treatment Period 1 or > 6.0 mg/dL during Treatment Periods 2, 3, 4, or 5, then the patient will be withdrawn from study drug based on the protocol deviation.

If withdrawn from study drug, the patient will continue study visits to the end of Treatment Period 6. At the discretion of the Investigator, the patient will be permitted to return to urate lowering therapy 60 days after the patient's last study drug treatment. Urate lowering therapy shall not be SEL-212 or KRYSTEXXA.

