08 JUN 2020

The Sponsor or the Sponsor's designee may request that the Investigator perform or arrange for the conduct of supplemental measurements and/or evaluations to elucidate as fully as possible the nature and/or causality of the AE or SAE. The Investigator is obligated to assist. If a patient dies during participation in the study or during a recognized follow-up period, the Sponsor will be provided with a copy of any post-mortem findings, including histopathology.

New or updated information will be recorded on the originally completed SAE forms, with all changes signed and dated by the Investigator. This information will also be entered into the CRF.

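### The protocol contradicts itself on whether AE and SAE collection and follow-up end about 30 days after the last dose or continue to the end of Treatment Period 6 in patients taken off study drug

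*Protocol*

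**What the plan says.** One group of passages stops at about 30 days after the last dose:

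- Protocol 12.2.4 (follow-up): "All AEs and SAEs will be followed until 30 days after the last dose of study drug, resolution of the event", with further endpoints ending "until the event is otherwise explained, or until the patient is lost to follow-up, whichever occurs earlier". SAEs and AESIs are not exempted.
- Protocol 12.2.3.1 (reporting period): "from the time the patient is dosed until the 30 days after the last infusion of study drug".
- Protocol 12.2.1.1: AEs and SAEs are collected until the End of Study Visit. The TEAE definition in that section places this visit 30 days after the last dose. SAP 8.3 repeats the definition.
- Protocol 7.1.3 and footnote 1 of Appendices A and C: the End of Study contact is a telephone call 30 (+4) days after the last infusion.
- Protocol 8.2.1.2: a patient is a completer on having "completed Safety Follow-up that occurs 30 (+ 4) days after the final dose of study drug".

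A second group continues to the end of Treatment Period 6:

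- Protocol 7.4.1.1, and the same sentence in 7.4.1.2: "If withdrawn from study drug, the patient will continue study visits to the end of Treatment Period 6". Section 8.2.1.3.1 also asks for data collection to that point.
- Appendices A and C mark AE/SAE collection as continuous across the treatment periods and schedule a gout flare assessment at every visit.
- Protocol 12.2.4, second paragraph: "All AEs and SAEs documented at a previous visit/contact and designated as ongoing will be reviewed at subsequent visits/contacts".

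Protocol 11.2.1 assesses gout flares as part of TEAE collection. SAP 7.2.5 analyses flares for Treatment Periods 1-3, 4-6 and 1-6.

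**The concern.** Because the earliest endpoint applies, 30 days after the last dose is a ceiling on follow-up even for an SAE that has not resolved. For patients who stop drug early, the same limit closes AE collection and declares study completion while most of their visits are still ahead. A site cannot obey both groups of passages, and different sites may settle the conflict differently.

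Two things are at stake. The first is safety data: a new event that starts after the 30-day limit, in a patient still attending visits, may or may not be recorded, and an SAE open at the limit may be closed administratively. The second is an efficacy endpoint. If flares enter the database through TEAE collection and the TEAE window has closed, flares in Treatment Periods 4-6 could be missing for patients stopped early, although those patients were seen and asked. The SAP does not say which rule prevails.

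**Working it through.** **The plan's own figure.** Protocol 7.1 gives total participation of 184 to 219 days (SEL-212) and 198 to 233 days (KRYSTEXXA). Inputs from the same section are screening of up to 45 days, last infusion on Day 140 or Day 154, and follow-up of 30 (+4) days.

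- Maximum: 45 + 140 + 34 = 219 and 45 + 154 + 34 = 233. Both are exact.
- Minimum: 14 + 140 + 30 = 184 and 14 + 154 + 30 = 198. These match only if screening lasts 14 days, which is an assumption; 7 days gives 177 and 191.

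The stated durations therefore describe fully dosed patients and are built on the 30 (+4)-day rule.

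**Earliest SUA-rule stops.** SEL-212 (7.4.1.1): a high value at Treatment Period 1 Day 21, so the last dose is Day 0. KRYSTEXXA (7.4.1.2): the Day 0 value does not count, so the first high pre-dose value is Day 14 and the optional check is Day 28 - 2 = Day 26. The last dose is then Day 14.

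**Gap for a withdrawn patient** = 168 - (last dose day + 30), where 168 is the end of Treatment Period 6.

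| Last dose | Limit | Gap (days) | Gap with +4 window |
|---|---|---|---|
| Day 0 (earliest SEL-212 SUA stop) | Day 30 | 138 | 134 |
| Day 14 (earliest KRYSTEXXA SUA stop) | Day 44 | 124 | 120 |
| Day 28 | Day 58 | 110 | 106 |
| Day 56 | Day 86 | 82 | 78 |
| Day 84 | Day 114 | 54 | 50 |
| Day 112 | Day 142 | 26 | 22 |
| Day 126 (KRYSTEXXA only) | Day 156 | 12 | 8 |
| Day 140 or later | Day 170 or later | none | none |

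For a last dose on Day 0, footnote 1 places the End of Study call at Day 30 to 34, before Treatment Periods 3 to 6 have begun.

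**Flare endpoint.** Treatment Periods 4-6 run from Day 84 (3 x 28) to Day 168, which is 84 days. The part inside the literal TEAE window is the limit minus 84:

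- last dose Day 0, 14 or 28: limit at or before Day 58, so 0 of 84 days;
- Day 56: 86 - 84 = 2 of 84;
- Day 84: 114 - 84 = 30 of 84;
- Day 112: 142 - 84 = 58 of 84;
- Day 140 or later: all 84.

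**Fully dosed patients.** The limits are Day 140 + 30 = 170 and Day 154 + 30 = 184, both past Day 168, so there is no visit gap. The ceiling in 12.2.4 still applies: an SAE starting 28 days after the last dose reaches it in 30 - 28 = 2 days.

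**The case against.** The strongest reply is that 12.2.4 should not be read from one sentence. Its second paragraph has ongoing events reviewed at later visits with no time limit, and a later paragraph adds that "The Sponsor or the Sponsor's designee may request that the Investigator perform or arrange for the conduct of supplemental measurements and/or evaluations", with which the investigator must assist. Section 12.2.3.2 requires SAE follow-up information within 24 hours of receipt and states no cut-off. Section 12.2.3.1 asks for notification of a related SAE learned of at any time after discharge. Section 12.2.2.4 has outcome codes for unresolved events, so such an event stays in the data. A reader might infer from the ceiling that unresolved SAEs are lost; the documents do not support that.

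This reply answers only part of the point. Review of ongoing events covers events already documented, not a new one starting after the limit, which 12.2.1.1 and 12.2.3.1 exclude. The sponsor's request is optional. The late-SAE clause is limited to related events, and investigators need not seek them actively.

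It is also fair to say that the gaps are lost safety time only if the 30-day passages prevail. If continuous collection in the schedules governs, nothing is lost. That is why the point is a contradiction and not a demonstrated loss of data.

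**Conclusion.** The contradiction is real and should be resolved. Its literal size is up to 138 days (SEL-212) or 124 days (KRYSTEXXA) of attended time for the earliest SUA-rule stops. It is 54 days for a last dose on Day 84, 26 days on Day 112 and none from Day 140. These figures assume nominal visit days and that the 30-day passages take precedence. A stop for another reason after the first dose would give 138 days in either arm.

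Two further inferences should not be drawn. A reader might use the planned non-response rates as a count of affected patients. But non-response is not the same as stopping drug: SAP 7.1 also counts study withdrawal and return to urate-lowering therapy as non-response, and patients may stop drug for adverse events, which those rates do not bound. A reader might also conclude that safety data are truncated unequally between arms. The 30-day rule is identical in both, and the documents give no frequency or timing of stopping by arm in this trial. With different stopping rules an imbalance is plausible, but it is not shown.

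The clearest possible effect on a reported result is on gout flares in Treatment Periods 4-6. For a last dose on or before Day 28, that whole period lies outside the literal TEAE window.

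**What to change.** 1. Reconcile Protocol 7.1.3, 8.2.1.2, 12.2.1.1, 12.2.3.1, 12.2.4 and footnote 1 of Appendices A and C (with their copies in the synopsis and SAP 3.8) with the schedules. AE/SAE collection and study completion should run to the later of 30 days after the last dose and the Treatment Period 6 Day 28 visit.
2. In 12.2.4, remove the 30-day limb as a ceiling for SAEs and AESIs still ongoing. Keep the other endpoints already listed: resolution, stabilisation, explanation and loss to follow-up.
3. In SAP 8.3, keep the 30-day TEAE tables unchanged and add a separate off-treatment column for later events.
4. In SAP 7.2.5, state that gout flares are counted through Treatment Period 6 whether or not they fall in the TEAE window.

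Dosing and stopping rules are untouched. The cost is amendment wording, one table column and some further contacts for the few SAEs ongoing at study end. Withdrawn patients need no extra visits for collection to Treatment Period 6 Day 28, because they are already scheduled to attend.
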